Comparison of cervical transforaminal epidural corticosteroid injections with lateralized interlaminar epidural corticosteroid injections for treatment of cervicogenic upper extremity radiculopathy

NCT03389620

Document Date: 11/15/2022

Purpose of the Study

Our central hypothesis is that the innovative CT fluoroscopy-guided lateralized interlaminar epidural corticosteroid injection technique will exhibit superior or equivalent efficacy to the traditional transforaminal method for treatment of cervicogenic upper extremity radiculopathy.

SPECIFIC AIM 1: Compare the efficacy of CT fluoroscopy-guided LILESI to that of CT fluoroscopy-guided TFESI in the treatment of patients with cervicogenic upper extremity radiculopathy.

HYPOTHESIS 1: Patient outcomes will be equivalent between the two injection techniques.

1.1 Compare the difference in the primary outcome measure between the two patient groups: numerical pain rating scale (averaged over the past 24 hours) at two months.

1.2 Compare the difference in secondary outcome measures between the two patient groups: numerical pain rating scale (averaged over the past 24 hours) at 2 weeks and 4 months; neck disability index, EQ-5D, and work ability index at 2 weeks, 2 months, and 4 months.

SPECIFIC AIM 2: Compare complication rates between the two injection techniques.

HYPOTHESIS 2: No difference will be seen in complication rates between the two injection techniques.

2.1 Determine the frequency of minor and major adverse events for each group immediately post-procedure and at 2 days after the procedure.

SPECIFIC AIM 3: Determine the technical success rate, defined as the spread of the contrast epidurogram into the neuroforamen, for each of the two injection techniques.

HYPOTHESIS 3.1: The contrast epidurogram will extend into the neuroforamen more frequently with the lateralized interlaminar approach than with the transforaminal approach.

3.1 Determine the frequency of contrast spread into the neuroforamen for each group.

HYPOTHESIS 3.2: Inadvertent intravascular injection will occur more frequently with the transforaminal approach.

3.2 Determine the frequency of inadvertent intravascular contrast injections for each group.

Background & Significance

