We will employ a single-center, parallel, randomized, prospective design. Enrolled patients will be assigned to one of two treatment arms using a block randomization scheme: transforaminal cervical epidural corticosteroid injection or lateralized interlaminar cervical epidural corticosteroid injection. Baseline data will be collected including duration, location, and character of pain; numerical pain scale (NRS); neck disability index (NDI); EQ-5D; and work ability index (WAI) (see Outcome Measures below). All procedures will be performed under CT fluoroscopy on the same scanner. The cervical level of injection for patients in both treatment arms will be at the discretion of the treating physician and will be based on symptoms (e.g., dermatomal distribution of pain) and imaging findings. All injections will be performed by a board certified radiologist with a certificate of added qualification in neuroradiology and at least five years of experience in CT fluoroscopy-guided spine injections. Patients and outcome assessors (clinical research coordinator) will remain blinded to the treatment assignment throughout

the study. In order to maintain blinding of patients and appropriate study personnel throughout the trial, billing / charges will be held until the patient reaches the final endpoint of the study or withdraws from the study. The research coordinator will be the study personnel who records the billing at this point, however, all outcome assessments will have been completed already ensuring that they remain unbiased. The treating physicians are unable to be blinded, as they will be aware of the type of patching material used. The effectiveness of patient blinding will be assessed using the Bang Blinding Index prior to discharge on the day of the procedure (8). Patients will become unblinded to their treatment assignment at the end of their participation in the study (either at the conclusion of the study after the final outcome measure time point (i.e. 4 months) or if they elect to withdraw from the study at any time).

Transforaminal Cervical Epidural Corticosteroid Injections (TFESI)

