Patients randomized to undergo LILESI will be placed prone on the CT gantry table. A planning CT will be obtained through the area of interest. Acquired images will allow for planning a posterior approach lateralized interlaminar needle trajectory to the dorsal epidural space. The skin surface will then be marked, sterilized, draped, and anesthetized. A 22-gauge 3.5 inch Quincke tip spinal needle will be advanced under intermittent CT fluoroscopic guidance into the lateral dorsal epidural space (Figure 2). On reaching the target, heme-negative aspiration will be confirmed. Next, approximately 0.2 mL of contrast material (iopamidol; Isovue-M 200, Bracco Diagnostics, Princeton, NJ) diluted 1:3 with preservative free normal saline will be injected to assess needle tip position and potential future medication spread. Intravascular injection will be excluded using a “double-tap” technique. After visual confirmation of correct needle tip position, 0.8 mL of dexamethasone (10 mg/mL) will slowly be injected over a period of approximately 30 seconds. On completion of the procedure, the patient will be observed for 30 minutes in the Radiology Observation unit.

Patient Outcome Measures

Prior to the procedure, baseline outcome measures of NRS, NDI, EQ-5D and WAI will be determined (see Outcome Measures below for description). Immediately post-procedure, NRS will be reacquired. NRS, NDI, EQ-5D and WAI will then also be acquired via mail, electronic communication, or telephone call at 2 weeks, 2 months, and 4 months post-procedure. The primary endpoint will be NRS (averaged over the past 24 hours) obtained at 2 months after the procedure. Secondary endpoints will include NRS at 2 weeks and 4 months after the procedure as well as NDI, EQ-5D and WAI at 2 weeks, 2 months, and 4 months after the procedure.

Adverse Events

Patients will be screened for adverse events immediately after the procedure as well as via phone call at 2 days post-procedure. While all adverse events will be recorded, the following will be considered major adverse events: stroke, paralysis, or other permanent neurologic deficit; allergic reaction; hospitalization or ER visit. Minor adverse events will include, but not be limited to: nausea / vomiting, dizziness, headache, symptomatic hypertension, vasovagal reaction, fever / chills, facial flushing, insomnia, and pain exacerbation.

Epidurogram

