The pain numerical rating scale (NRS) is a well-validated tool for quantitatively assessing patients' pain (12). The NRS asks patients to rate their current pain intensity on an 11-point scale ranging from 0 ("no pain") to 10 ("worst possible pain"). It has been found to be a valid measure of pain intensity with minimum clinically important difference noted to be a change of 2 points (13, 14). We will use NRS averaged over the past 24 hours for all time points in this trial. The Initiative on Methods, Measurement, and Pain Assessment in Clinical Trials (IMMPACT) consensus statement indicates that an NRS reduction of 30% (or 2 points) is associated with a meaningful or moderately important improvement in pain. Further, IMMPACT also indicates that an NRS reduction of 50% (or 4 points) is associated with a substantial improvement in pain. We will follow their consensus recommendations and explicitly report these two categories of pain relief (15).

Neck Disability Index (NDI)

The NDI a well-validated measurement tool that contains 10 items: seven related to activities of daily living, two related to pain, and one related to concentration (16). Each item is scored from 0 to 5 and the total score is expressed as a percentage, with higher scores corresponding to greater disability. The NDI has documented acceptable levels of responsiveness and construct validity when used in patients with cervical radiculopathy (17).

EQ-5D

EQ-5D is a standardized measure of health status developed by the EuroQol Group in order to provide a simple, generic measure of health for clinical and economic appraisal (18). It is a well-validated tool for health status measurement (19), and for health quality-of-life in cervicogenic radicular pain (20).

Work Ability Index

The Work Ability Index (WAI) is a validated, reliable measure of a worker's ability to do his or her job that has been shown to predict work disability, retirement and mortality (21). The questionnaire demonstrates excellent test - retest reliability (22).

All data will be collected in a password-protected file and will be stored in an electronically secure environment, as specified in the research data security plan (RDSP).

Selection of Subjects

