Based on a power of 0.8 (alpha 0.05) to detect superiority of the LILESI group, assuming positive response rates of 45% for the TFESI group and 70% for the LILESI group, we would need a total of 116 patients (57.5 patients in each arm). This sample size would also give us a power of 0.99 to detect non-inferiority (i.e. equivalence between TFESI and LILESI) (non-inferiority margin 0.1).

Patient Outcome Analysis

A reduction of 2 points from baseline on the NRS will be considered a positive response (clinically meaningful or moderate improvement per IMMPACT consensus statement) (15). Primary Endpoint (average NRS over the past 24 hours at 2 months time point): We will apply a difference test and a non-superiority test for binomial proportion to test the primary endpoint. Secondary Endpoints: The secondary endpoints will be analyzed using a test for difference in binomial proportions or a t-test for binomial or semi-continuous variables, respectively.

Interim Data Analysis

An interim analysis will be performed of the first 58 patients by the biostatistician (co-investigator). All study participants, assessors, and other personnel (including other co-investigators) will remain blinded. Safety and efficacy will be evaluated using an O'Brien–Fleming stopping rule of $p < 0.001$ for the interim analysis in order to evaluate for early evidence of treatment efficacy (26).

Crossover, Withdrawal, or Missing Data

We will employ an intention-to-treat (ITT) analysis for this trial (27). Patients that crossover between study arms, withdraw from the study, or for whom there is missing data will all be handled in the same manner. A conservative approach will be taken and we will assume that the patient will receive no further benefit from the study injection. As such, the most recent available outcomes data will be extrapolated to all later time points for which no data are available.

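### The only method the plan offers for NDI, EQ-5D and WAI is a t-test, with no baseline adjustment and no choice between follow-up and change scores, although every scale is measured at baseline

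*Combined protocol and SAP*

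**What the plan says.** Under Data Analysis & Statistical Considerations, Patient Outcome Analysis, the secondary analysis is one sentence: "The secondary endpoints will be analyzed using a test for difference in binomial proportions or a t-test for binomial or semi-continuous variables, respectively". It does not say which endpoints fall under which test.

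The secondary endpoints are NRS at 2 weeks and 4 months, plus the three other scales. Specific Aim 1 lists these as "neck disability index, EQ-5D, and work ability index at 2 weeks, 2 months, and 4 months".

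Baselines exist for all of them. Patient Outcome Measures states: "Prior to the procedure, baseline outcome measures of NRS, NDI, EQ-5D and WAI will be determined". The first section of Design & Procedures lists the same four scales among the baseline data.

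The analysis section uses a baseline in one place only, the NRS responder definition: "A reduction of 2 points from baseline on the NRS will be considered a positive response". The NRS description under Outcome Measures also commits to two categories of pain relief. Nothing similar is given for the other scales. NDI, for example, is described only as a score: "Each item is scored from 0 to 5 and the total score is expressed as a percentage". The documents mention no ANCOVA, regression, mixed model or covariate.

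**The concern.** There are two gaps in the same sentence.

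- **Specification.** A t-test on follow-up scores and a t-test on changes from baseline both comply with the text, yet they can give different estimates and p-values from the same data. The choice stays open until the data are seen.
- **Precision.** The baseline of each scale is collected and then left out, or, if changes are used, entered with a fixed coefficient of 1 that may be far from the best one. Specific Aim 1 hypothesises equivalent outcomes, so the width of the interval for each scale is much of the evidence, and a non-significant t-test is not.

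Neither t-test biases the treatment comparison under randomisation. The primary responder analysis is consistent with the NRS description and is not questioned here.

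**Working it through.** **Plan's own figure.** For 45% versus 70%, two-sided alpha 0.05, power 0.80 and unpooled variance: (1.960 + 0.842)² × (0.45×0.55 + 0.70×0.30) / 0.25² = 57.45 per arm, so 58 per arm and 116 in total. This reproduces the stated 116. It rests on the NRS responder endpoint; the plan has no planning figure for NDI, EQ-5D or WAI.

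**Comparisons affected.** NDI, EQ-5D and WAI at three times each: 3 × 3 = 9. NRS at two times: 2. Total 11. The two NRS endpoints most naturally go to the proportion test, because only NRS has responder thresholds, but the plan does not say so.

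**Inputs.** n = 58 per arm, from the plan. The rest is assumed, because the documents give no SD, correlation or effect size for these scales:
- follow-up SD set to 1;
- r, the correlation of baseline with follow-up: 0.3, 0.5, 0.7;
- k, baseline SD divided by follow-up SD: 1, 0.7, 0.5;
- a true difference of 0.5 follow-up SD for power.

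**Variance of the treatment difference.**
- Follow-up scores: 2/58.
- Change scores: (2/58)(1 + k² − 2rk).
- ANCOVA: (2/58)(1 − r²), times 113/112 for chance baseline imbalance.

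Apart from the 113/112 factor, the ANCOVA variance is below the follow-up variance by r² (in units of 2/58) and below the change variance by (1 + k² − 2rk) − (1 − r²) = (k − r)². Neither can be negative. Change scores beat follow-up scores only if k² − 2rk < 0, that is k < 2r, which is not known in advance.

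**95% CI half-width and power.** The half-width is t × √variance, with 114 df for the t-tests and 113 for ANCOVA. For follow-up scores: 1.981 × √(2/58) = 0.368. Power uses the noncentral t distribution.

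| Analysis | Half-width in SD, r = 0.3 / 0.5 / 0.7 | Power at 0.5 SD |
|---|---|---|
| Follow-up t-test | 0.368 / 0.368 / 0.368 | 0.76 / 0.76 / 0.76 |
| Change t-test, k = 1 | 0.435 / 0.368 / 0.285 | 0.62 / 0.76 / 0.93 |
| Change t-test, k = 0.7 | 0.381 / 0.327 / 0.263 | 0.73 / 0.85 / 0.96 |
| Change t-test, k = 0.5 | 0.359 / 0.319 / 0.273 | 0.78 / 0.87 / 0.95 |
| ANCOVA | 0.353 / 0.320 / 0.264 | 0.80 / 0.87 / 0.96 |

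**Variance removed by ANCOVA** (before the 113/112 factor).
- Against follow-up scores, r²: 9% / 25% / 49%.
- Against change scores, 1 − (1 − r²)/(1 + k² − 2rk): 35% / 25% / 15% at k = 1; 15% / 5% / 0% at k = 0.7; 4% / 0% / 7% at k = 0.5.

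**Most that ANCOVA can cost.** At r = 0 its half-width is 0.3695 against 0.3679 for follow-up scores, a ratio of 1.0045, or about 0.5% wider.

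**Effect of leaving the choice open.** Under no difference, the follow-up and change statistics correlate at (1 − rk)/√(1 + k² − 2rk). If the smaller of the two p-values were always reported, the bivariate normal false-positive rate per endpoint would be about 9% at k = 1, 8% at k = 0.7 and 7% at k = 0.5, instead of 5%. This is a worst case; nothing in the documents suggests that it is intended.

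**The case against.** The strongest reply is that an unadjusted t-test on a randomised secondary endpoint is unbiased and widely accepted, so asking for ANCOVA is a preference for efficiency and corrects no error. That stands, and it limits how hard the point can be pressed. It does not answer which t-test is meant.

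On that, the endpoints are named as scales at fixed times and change is never mentioned for NDI, EQ-5D or WAI, so follow-up scores are the plainer reading. But the primary endpoint is also named as NRS at a fixed time and is then analysed as a response relative to baseline, so the wording does not settle it.

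Assigning the three scales to the t-test is an inference. It is a firm one, since no cut-off is defined for any of them.

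The sizes rest on assumed r, k and effect. Several cells show almost no gain over change scores, and the 49% needs r = 0.7 with follow-up scores. The figures illustrate a range and do not predict this trial.

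Three details also stand. WAI may be unusable for patients who do not work, so 58 per arm may be optimistic for it. The plan does not say which EQ-5D score is analysed. ANCOVA needs a baseline value, and carrying later values forward does not supply a missing one. The first two apply equally to the t-test. The third should be rare, because baselines are taken before the procedure.

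**Conclusion.** The concern holds. The plan leaves the analysis of nine of its 11 secondary comparisons open between two t-tests and makes no planned use of the baselines as covariates. The consequence is moderate: no bias, and no effect on the primary conclusion or on the 116 patients. For r from 0.3 to 0.7 and k from 0.5 to 1, ANCOVA removes from about 0% to 49% of the variance, depending on which t-test it replaces. At r = 0.5 its interval is 13% narrower than that for follow-up scores (0.320/0.368 = 0.87). Since k < 2r cannot be checked beforehand, neither t-test is the safe choice, whereas ANCOVA matches or beats both apart from one degree of freedom. The change should be made, as a nearly free improvement and not as the repair of an invalid analysis.

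**What to change.** In Patient Outcome Analysis, replace the t-test clause with wording such as:

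> For each of NDI, EQ-5D and WAI, and at each follow-up time, the arms will be compared by ANCOVA of the follow-up score on treatment arm and the baseline score of the same scale. The adjusted mean difference will be reported with its 95% CI.

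Add a phrase saying whether the two secondary NRS endpoints are 2-point responder proportions or scores; if scores, use the same ANCOVA.

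Leave the responder primary, the 0.1 margin and the 116 patients unchanged. No further analysis of NRS at 2 months is needed. The cost is one or two sentences and one degree of freedom per model, with no new data.

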The primary investigator will retrospectively evaluate epidurographic contrast material spread through review of the procedural images at the completion of the study. The leading edge of resultant contrast during both the TFESI and LIESI groups will be categorized as either within the spinal canal, intraforaminal, or extraforaminal, as previously described in publications by our group (see Figure 1B) (11). The presence of inadvertent intravascular injection will also be noted, as previously described by our group (10).

Crossover, Withdrawal, or Missing Data

We will employ an intention-to-treat (ITT) analysis for this trial [49]. All persistently symptomatic patients, regardless of study arm (i.e. both LIESI and TFESI), will be allowed to crossover at the 2-month time point. Patients that crossover between study arms, withdraw from the study, or for whom there is missing data will all be handled in the same manner: we will conservatively assume that no further benefit will be gained from the initial treatment. As such, the most recent available outcomes data will be extrapolated to all later time points for which no data are available. Patients will be allowed to withdraw from the study and terminate their participation at any time.

Interim Data Analysis

An interim analysis will be performed of the first 58 patients by the biostatistician. All study participants, outcome assessors, and other personnel will remain blinded. Safety and efficacy will be evaluated using an O'Brien–Fleming stopping rule of $p < 0.001$ in order to evaluate for early evidence of treatment efficacy [48].

Outcome Measures

Numerical Rating Scale (NRS)

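### Intention-to-treat with the last value carried forward is the only analysis of the non-inferiority test, and calling it conservative does not hold for that test

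*Combined protocol and SAP*

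**What the plan says.** The section Crossover, Withdrawal, or Missing Data appears twice in the combined protocol and SAP, under Design & Procedures and under Data Analysis & Statistical Considerations. Both versions give the same rule.

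- Analysis set: "We will employ an intention-to-treat (ITT) analysis for this trial (27". No per-protocol or as-treated set is defined.
- Scope: "Patients that crossover between study arms, withdraw from the study, or for whom there is missing data will all be handled in the same manner".
- Imputation: "the most recent available outcomes data will be extrapolated to all later time points for which no data are available".
- Justification: "A conservative approach will be taken and we will assume that the patient will receive no further benefit from the study injection".
- Crossover (Design & Procedures version only): "All persistently symptomatic patients, regardless of study arm (i.e. both LIESI and TFESI), will be allowed to crossover at the 2-month time point".

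The primary endpoint falls at the same time as permitted crossover: "The primary endpoint will be NRS (averaged over the past 24 hours) obtained at 2 months after the procedure". It is analysed as a responder proportion: "A reduction of 2 points from baseline on the NRS will be considered a positive response". Sample Size Determination powers a superiority test and then claims a "power of 0.99 to detect non-inferiority (i.e. equivalence between TFESI and LILESI", with a margin of 0.1. Hypothesis 1 is that outcomes are equivalent. No sensitivity analysis for missing data is planned.

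**The concern.** The argument for calling the rule conservative fits a superiority test. If imputation shrinks the apparent difference between arms, superiority becomes harder to show. For non-inferiority the same shrinkage works the other way, because a true deficit for LILESI looks smaller and the margin is easier to clear.

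The carried value may also not be free of benefit. NRS is collected on the day of the procedure and at 2 weeks. If relief fades by 2 months, carrying either score credits the patient with a response that has gone.

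Two kinds of patient can produce this at 2 months: those with no 2-month score, and those who did not receive the assigned route or had other treatment first. The first matters more. Follow-up is remote, withdrawal is allowed at any time, and the recruitment target of 116 equals the calculated sample size, so there is no allowance for dropout.

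At stake is whether a finding of non-inferiority could come from how missing scores were filled in. With one analysis only, a reader could not tell.

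**Working it through.** **Inputs from Sample Size Determination.** Response 45% (TFESI) and 70% (LILESI); alpha 0.05; power 0.8; 116 patients in total, so 58 per arm; margin 0.1; non-inferiority power 0.99.

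**Assumed, because the documents do not say.** An unpooled z-test; one-sided 0.05 for non-inferiority, with 0.025 shown beside it; and all rates of missing scores, non-delivery and carried response.

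**1. The plan's own figures.** Superiority, two-sided 0.05:

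n per arm = [0.45×0.55 + 0.70×0.30] × (1.96 + 0.8416)² / 0.25² = 0.4575 × 7.849 / 0.0625 = 57.45, rounded up to 58, total 116. This matches.

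Non-inferiority power: SE = √(0.4575/58) = 0.0888; (0.25 + 0.10)/0.0888 = 3.94; Φ(3.94 − 1.645) = 0.989 at one-sided 0.05, or Φ(3.94 − 1.96) = 0.976 at one-sided 0.025. The stated 0.99 fits one-sided 0.05 best.

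**2. False non-inferiority rate with complete data.** Set the truth at the margin: TFESI 45%, LILESI 35%. The test statistic is

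Z = (p_L − p_T + 0.1) / √{[p_L(1 − p_L) + p_T(1 − p_T)]/58}.

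Summing exact binomial probabilities over all outcomes that pass gives 0.055 at one-sided 0.05 and 0.026 at one-sided 0.025. These are the reference values.

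**3. What imputation does to the gap.** If a fraction d of each arm is imputed and the carried values differ by g (LILESI minus TFESI), the expected gap is

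−0.10(1 − d) + g·d = −0.10 + d(0.10 + g).

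The gap narrows if g is above −0.10, is unchanged at g = −0.10, and widens below it. For switching of a fraction d in both arms, the gap is −0.10(1 − 2d).

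**4. Results** (same exact enumeration, 58 per arm):

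| Assumed scenario | TFESI | LILESI | Gap | Rate, 0.05 | Rate, 0.025 |
|---|---|---|---|---|---|
| No dilution | 45% | 35% | −10.0 | 0.055 | 0.026 |
| 5% of each arm receive the other route | 44.5% | 35.5% | −9.0 | 0.068 | 0.033 |
| 10% carried, no difference between arms | 40.5% | 31.5% | −9.0 | 0.067 | 0.033 |
| 20% carried, no difference between arms | 36% | 28% | −8.0 | 0.081 | 0.044 |
| 10% carried, 65% v 55% | 47% | 37% | −10.0 | 0.054 | 0.026 |
| 20% carried, 65% v 55% | 49% | 39% | −10.0 | 0.052 | 0.027 |
| 10% carried, 65% v 40% | 47% | 35.5% | −11.5 | 0.038 | 0.017 |
| 20% carried, 65% v 40% | 49% | 36% | −13.0 | 0.026 | 0.012 |
| 10% (TFESI) and 20% (LILESI) missing, all non-response | 40.5% | 28% | −12.5 | 0.028 | 0.013 |

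The two no-difference rows take every carried value as a non-response in both arms. A common carried response of 50% gives 0.068 and 0.082 instead, so the result depends little on that level.

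**The case against.** **Direction.** A reader might infer that this analysis necessarily favours non-inferiority. The documents do not support that. They give no rate of missing data, no balance between arms, and nothing on which score would usually be carried. Step 3 shows that the sign depends on g. Only the TFESI description includes a lidocaine test injection, so a carried same-day score could favour TFESI and work against LILESI. This objection stands.

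**The rule modelled.** The plan carries the latest score; it does not count missing as non-response. An injected patient will usually have a same-day or 2-week score. The no-difference rows are therefore illustrations of equal carried response, not predictions.

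**Crossover.** A reader might also infer that crossover dilutes the primary endpoint. Permitted crossover opens only at 2 months, so it should not, provided NRS is taken first. The documents do not state that order.

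**Route switching.** Treatment is one image-guided injection by experienced operators, and no same-day conversion is described. Switching of 10% or 20% in both arms, which would give 0.084 or 0.123, has no basis in the text. At 2% the rate is 0.060.

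**The remedy.** A per-protocol set can itself be lenient. If 10% of LILESI and 5% of TFESI patients are excluded and all are failures, the rates become 0.35/0.90 = 38.9% and 0.45/0.95 = 47.4%. That gap is 8.5 points, against a true 10. Per-protocol analysis alone is therefore not enough.

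**Role of the test.** The sample size is built on superiority, with non-inferiority added. That is true, but Hypothesis 1 is equivalence and the plan claims power for non-inferiority, so the test needs support.

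**Conclusion.** The point holds in a limited form. The plan's single analysis is not conservative for the non-inferiority test, and nothing in the plan would reveal whether it had helped or hindered that conclusion. At one-sided 0.05, the assumed scenarios move the false non-inferiority rate from 0.055 up to between 0.067 and 0.081, or down to between 0.026 and 0.038, according to how carried values differ between arms. These figures rest on an unpooled z-test, truth exactly at the margin, and departure rates that the documents do not give. Missing 2-month scores are the main concern; failure to deliver the assigned route is secondary. The documents do not support saying that bias toward non-inferiority is certain or large, or that per-protocol analysis should replace intention-to-treat.

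**What to change.** In Data Analysis & Statistical Considerations, keep intention-to-treat as the primary analysis and remove the conservative label as justification for the non-inferiority test. Make the matching edit in the Design & Procedures version. Pre-specify two supporting analyses of that test:

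- **(a) Per-protocol:** assigned route delivered, no other cervical injection or surgery before the 2-month score, and 2-month NRS observed.
- **(b) Intention-to-treat with multiple imputation in place of carry-forward:** impute 2-month NRS from baseline and the other collected scores, then derive response. Include a version in which missing LILESI outcomes are imputed with a response probability lower by the 0.1 margin.

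Claim non-inferiority only if these are consistent with the primary result, and say in advance what consistent means (for example, each lower confidence limit for LILESI minus TFESI also lies above −0.1). State that the 2-month NRS used in the primary analysis is the one recorded before any crossover, and state the one-sided alpha.

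**Cost:** some extra analysis, largely of data already to be collected; delivered route and any other treatment before 2 months must be recorded. The per-protocol set is smaller and not fully protected by randomization, so it accompanies intention-to-treat and does not replace it. Under the plan's 45% and 70%, the power of the per-protocol test at one-sided 0.05 falls from 0.989 to 0.982 if 10% are excluded, or 0.970 if 20% are.
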